## C] Interventions:

➤ **Medical History Questionnaire:**

For every patient, to exclude the presence of any systemic condition interfering with orthodontic treatment.

➤ **Clinical Examination:**

Oral structures will be examined to identify caries, fracture or missing teeth. Gingival tissues will be carefully examined for any gingivitis, periodontitis, recession, or lesions.

> **Diagnosis**

Check the potential patient to fulfill the previously mentioned inclusion criteria. Every participant will be asked to sign an informed consent about the study. Full set of records (study models, panorama radiograph and lateral cephalometric radiographs, photos) will be taken for every patient as part of the routine procedure for treatment of patients in the clinic of the Orthodontics and Dentofacial Orthopedics Department, Future University in Egypt.

> **Clinical Procedure:**

After taking pre-treatment records, every patient will receive:

- Bonding of all teeth except for first premolars and banding/bonding the first and second molars will be done using Roth prescription brackets (0.022 x 0.028 slot)\*.
- Miniscrews will then be placed in the upper arch between the second premolar and first molar\*\*.
- The patient will be referred for extraction of first premolars.
- Anchorage will be secured, followed by Leveling and alignment for the bonded and banded teeth through following the wire sequence: 0.014 Nitti, 0.016×0.022 Nitti and 0.017×0.025 StSt.

- After levelling and aligning is completed (right before retraction), the patient will be referred for the uptake of pre-intervention records:
  - a- CBCT
  - b- Impression and models
  - c- photo (Extraoral & Intraoral)
  - d- pain questionnaire

➢ **Acquisition of pre-intervention records:**

- The patient will be referred for the uptake of a CBCT, which are considered to be the T0 records.
- Impressions will be taken before retraction (without the archwire in place) followed by digital scanning of produced models.
- Photos (Extraoral & Intraoral)
- Pain questionnaire distributed with explanatory session on it

➢ **Beginning of Retraction:**

*Frictionless group:*

- A braided ligature wire extended between the second premolars and miniscrews will be used for proper indirect anchorage control.
- Closing retraction T-loops will be fabricated using 0.017 x 0.025 TMA wire. The loop will be positioned halfway the extraction space and the canine. [40,41].
- A gable angle of 45° will be added to the posterior segment.

- Distal activation of 4 mm will be applied with cinching back the wire to the auxillary tube distal to first molars bilaterally. [42]

***Friction group:***

- Crimpable hooks added to the arch wire (0.017"x0.025" Stainless steel) distal to the lateral incisor passing near the center of resistance of the anterior segment.
- A ligature wire extending between the second premolar and miniscrews will be used for proper anchorage control.
- Retraction will start on a 0.017"x0.025" Stainless steel wire using elastomeric chain (force applied will be 200 g per side) [43] extending between the crimpable hooks and the miniscrews.
- The force will be measured by a force gauge and reactivated every 4 weeks maintaining constant force of retraction all over the retraction phase.

➢ **Follow up visits**

Patients will be asked to attend for follow up sessions every 4 weeks for:

- Evaluation miniscrews stability.
- Replacement of the power chain to maintain a force of 200 gm per side.
- Reactivation of the T-loop by further distal activation and cinch back.
- Impression taking to determine the anchorage loss

➤ **Criteria for discontinuing or modifying the allocated intervention:**

In cases of prolonged swelling or pain related to the miniscrews, the patient will be given strict oral hygiene measures and may wait for three weeks before the beginning of retraction.

In cases of loose or broken miniscrews, the screw will be removed and replace the miniscrew after total resolution of the inflammation.

➤ **Criteria for Ending the retraction:**

a-class I canines

b-normal overjet

c- closure of extraction space

d- reaching good profile

Ø **Post-retraction Questionnaire:**

The patients of both groups will be asked to fill in questionnaires regarding their experience with their allocated technique during the whole retraction period from day of extraction till the end of retraction.

Ø **Retraction records**

Following “En-masse retraction”, patients will be referred to the same radiology center to acquire the final cone-beam CT to assess the movement and inclination of anterior teeth.

The final dental model will be used to assess the rate of retraction and molar anchorage loss achieved throughout the study.

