## **Rationale for carrying out the trial:**

The main reasons of extraction in orthodontics is to correct severe crowding, achieve proper facial profile, improve lip competence and to adjust buccal relationships[1-3]

At the beginning, first premolars are extracted , initial bonding is done followed by leveling and alignment procedures. After this step, there are two general techniques to retract the six anterior teeth with less mesial drifting of the maxillary first permanent molar.

The first approach is a regular procedure where the canines and incisors are retracted in two separate steps. Primary, the canine in the extraction quadrant is retracted until it comes in contact with the tooth distal to the extraction space then canines are anchored to the teeth distal to them where they are used as single

anchor units to retract the incisors. This procedure is called “Two-step retraction” technique.[4-6]

The main advantage of this approach is that the load on the posterior teeth is reduced, thus minimal anchorage loss would be expected. The second step, where the posterior segments are anchored with the canines to retract anterior teeth without loosing anchorage [7].However, Closing the extraction space in two steps increases treatment time and also the medial displacement tendency of maxillary first molars is high, thus requiring further time and effort [8]

A second technique was introduced to overcome the disadvantage of the “Two-step retraction” technique where the incisors and canines are retracted separately. This approach is called “En-masse retraction”. Bennett and McLaughlin developed the MBT system in which they used this technique [9,10].

“En-masse retraction” technique has become popular because of its simplicity, but theoretically might be expected to have more load on the posterior segment than the "Two-step retraction" technique.

The use of Temporary Anchoring Devices (TADs) as anchorage is superior to conventional molar anchorage in maximum anchorage and hence attaining better treatment [11,12,13]

Space closure is a tough process in orthodontics, as it requires a strong basis of biomechanics in order to close a space efficiently with minimal unwanted side effects. It can be done with two forms of mechanics: Friction or Frictionless mechanics.

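### The two arms anchor the retraction force at different places, so a difference in anchorage loss belongs to the two complete systems and cannot be credited to frictionless or friction mechanics alone

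*Protocol*

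**What the plan says.** **Aims.** Under Aim of the study, Intervention and Comparator each pair a type of mechanics with miniscrew anchorage, and the anchorage phrase is the same in both. The aim at the end of the Rationale, the Research question, the Research hypothesis and the Primary objective all present frictionless versus friction mechanics as what is being compared on anchorage loss. Study design also defines the arms by their mechanics and says that the interventions will be compared on anchorage loss.

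**Procedures (section C, Interventions).** Every patient has miniscrews at the same site in the upper arch.

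- Frictionless group: "A braided ligature wire extended between the second premolars and miniscrews will be used for proper indirect anchorage control". The loop is then loaded as follows: "Distal activation of 4 mm will be applied with cinching back the wire to the auxillary tube distal to first molars bilaterally". Under Follow up visits this is repeated: "Reactivation of the T-loop by further distal activation and cinch back".
- Friction group: "A ligature wire extending between the second premolar and miniscrews will be used for proper anchorage control". In addition, retraction is done "using elastomeric chain (force applied will be 200 g per side) [43] extending between the crimpable hooks and the miniscrews", and the chain is replaced at follow-up visits.

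**The concern.** Anchorage loss is the primary outcome, and the place where the retraction force is anchored can plausibly act on it directly. If that place changes together with the mechanics, a significant result is a result for the pair of features. Read as the question and hypothesis are worded, it would be credited to the mechanics. A non-significant result has the same weakness: an effect of mechanics and an opposite effect of the anchor could offset each other and be reported as no difference between mechanics.

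Randomisation does not help, because it balances patients and not two features that always go together within an arm. A larger sample does not help either.

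**Working it through.** No figure in the plan is in dispute here; the sample size calculation plays no part. The check sets the passages side by side.

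**Step 1. What is common and what differs (Interventions).**

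| Feature | Frictionless arm | Friction arm |
|---|---|---|
| Miniscrew site | same | same |
| Ligature from second premolar to screw | yes | yes |
| Retraction force anchored on | posterior teeth (wire cinched distal to first molars) | the miniscrew (chain from crimpable hooks) |
| Renewed at follow-up visits | further activation and cinch back | new chain |

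The word indirect is the Protocol's own, used for the frictionless arm. That the screw bears the chain's force directly in the friction arm is inferred from where the chain is attached.

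**Step 2. What the trial can estimate.** Write μ(mechanics, anchor) for mean anchorage loss. The trial observes two combinations: μ(frictionless, teeth) and μ(sliding, screw). The estimated difference is

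D = μ(frictionless, teeth) − μ(sliding, screw).

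Adding and subtracting μ(sliding, teeth) gives

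D = [μ(frictionless, teeth) − μ(sliding, teeth)] + [μ(sliding, teeth) − μ(sliding, screw)].

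The first bracket is an effect of mechanics with the anchor held fixed; the second is an effect of the anchor under sliding. No arm supplies μ(sliding, teeth), so only the sum can be estimated. More patients reduce the standard error of D but say nothing about the split.

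**Step 3. Is the second bracket more than a formality in this Protocol?**

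- The Literature Review, in the part on CBCT landmarks for anchorage loss, describes a canine-retraction study that used sliding mechanics with a micro-implant on one side and the molar as anchor on the other. Sliding mechanics therefore does not by itself fix the anchor.
- The Rationale treats the source of anchorage as relevant: "The use of Temporary Anchoring Devices (TADs) as anchorage is superior to conventional molar anchorage in maximum anchorage". It also ties anchorage loss to posterior segments that are not well stabilised.
- The inclusion criteria admit only cases that need maximum anchorage.

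**Step 4. Size.** The documents contain no comparison of a force anchored on a screw with a force anchored on posterior teeth that are themselves tied to a screw. No estimate can be derived, and the effect could be nil.

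**The case against.** The strongest reply is that nothing in the PICO is false. Both arms do use miniscrews as anchorage, the ligature is shared, and no sentence claims that the screw is used in the same way in each arm. Study design speaks of comparing interventions, and other sections speak of techniques or methods. It can also be argued that the point of attachment is part of how each mechanic is delivered: a loop is activated through its wire, a chain by stretching it to an attachment. The documents do not say whether a T-loop could be loaded directly from a screw.

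Much of this stands. There is no literal contradiction, and comparing two complete systems is a legitimate design. What remains is that the PICO names anchorage separately from mechanics and in identical words, that Study design does not mention the different anchor, and that the question and hypothesis carry the mechanics label alone.

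A reader might infer four stronger things that the documents do not support:

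- *That the arms differ in how the screw supports the posterior teeth.* That support is the premolar ligature, and both arms have it. The chain runs from anterior hooks to the screw.
- *That features such as "Closing retraction T-loops will be fabricated using 0.017 x 0.025 TMA wire" or the gable bend that "will be added to the posterior segment" are further confounders.* The Rationale presents loop design as the means by which frictionless mechanics control movement, so these belong to the intervention.
- *That the 2 mm average difference quoted in the Literature Review measures the problem.* It compares screws with conventional anchorage; here both arms have a screw.
- *That the randomised comparison is invalid.* It is valid for the two set-ups as described.

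**Conclusion.** The point holds as one of attribution. The trial can show whether anchorage loss differs between two complete retraction systems. It cannot show how much of a difference, or of an apparent lack of one, is due to the mechanics and how much to the place where the retraction force is anchored. The size and direction of any anchor effect are unknown. The conclusion rests on reading Interventions as written: chain attached to the screw in one arm, wire cinched distal to the first molars in the other. It also assumes that the place of anchorage may affect anchorage loss, which the Protocol's own rationale makes plausible but does not quantify. The matter should be corrected because it bears on how the primary result will be stated, but it does not threaten the comparison itself.

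**What to change.** Reconcile the aim in the Rationale, the PICO, Research question, Research hypothesis and Primary objective with the procedures in section C. No clinical set-up is recommended here. If the set-ups stay as described:

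1. State in the PICO, question, null hypothesis and objective where the retraction force is anchored in each arm. For example, *Intervention: T-loop system, force anchored on the posterior teeth by cinching distal to the first molars, with indirect screw support through a premolar ligature. Comparator: sliding system, force anchored on the miniscrew by the chain, with a premolar ligature to the screw.*
2. Define the contrast as two complete retraction systems including their anchorage.
3. Add: *A difference, or no difference, in anchorage loss will be reported as between the two systems and will not be attributed to friction or its absence alone.*

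The cost is wording only: procedures, sample size and analysis are unchanged. The downside is a narrower and less general claim.

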## **Secondary objective:**

Evaluating the rate of “En-masse retraction” using frictionless Versus friction mechanics, root resorption, pain and discomfort during retraction. In addition to this, changes in vertical position (extrusion/ intrusion), tip and torque of anterior teeth will be measured following “En-masse retraction” using frictionless versus friction mechanics.

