## D] Outcomes

[figure not shown]
**Primary outcome:** is to monitor the anchorage loss during “En-masse retraction”. All outcomes will be assessed as the difference between T0 at the start of retraction and T1 after complete space closure.

**Secondary outcomes:** is to monitor the changes in the anterior teeth position (final anterior teeth tip, torque and vertical position), rate of space closure, presence of any root resorption and pain associated with the different methods used for retraction.

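### The post-retraction questionnaire covers the time from premolar extraction, while the pain objective and the T0–T1 outcome window begin at the start of retraction

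*Protocol*

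**What the plan says.** The secondary objective covers "root resorption, pain and discomfort during retraction". D] Outcomes names the outcome as "pain associated with the different methods used for retraction" and sets one window for everything: "All outcomes will be assessed as the difference between T0 at the start of retraction and T1 after complete space closure".

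The post-retraction questionnaire in C] Interventions uses a different window. Patients report "their experience with their allocated technique during the whole retraction period from day of extraction till the end of retraction".

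The clinical procedure in the same section fixes the order of events for every patient. After bonding and miniscrew placement, "The patient will be referred for extraction of first premolars". Then "Anchorage will be secured, followed by Leveling and alignment for the bonded and banded teeth", through a three-wire sequence common to both groups. Only then are the T0 records taken: "After levelling and aligning is completed (right before retraction), the patient will be referred for the uptake of pre-intervention records". E] Participant timeline (items 6 to 9) gives the same order and separates the arms at retraction, by power chain or T-loop.

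Two other places describe the questionnaire without narrowing it. E] Participant timeline, item 12, refers to the patient's experience during treatment. The pain item under A] Data collection methods refers to pain and discomfort over the whole trial.

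**The concern.** The questionnaire window opens at extraction. The outcome window opens at T0, after levelling is complete. Between those two points nothing in the protocol differs between the arms, so pain from that stretch says nothing about T-loops versus power chain. If it enters the reported score, it dilutes whatever difference retraction produces.

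At stake is whether the pain result answers its own objective. If no difference were found, one could not tell two equally painful techniques from a real difference masked by shared earlier pain. The introduction gives the shortage of studies on pain and satisfaction as part of the rationale, so the outcome is not incidental. Once patients have answered about the longer window, no analysis can separate the phases.

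**Working it through.** **1. The windows side by side**

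| Place in protocol | Window opens | Window closes |
|---|---|---|
| Secondary objective | start of retraction | end of retraction |
| D] Outcomes | T0, start of retraction | T1, complete space closure |
| C] Interventions, post-retraction questionnaire | day of extraction | end of retraction |
| E] Participant timeline, item 12 | not limited (treatment) | not limited |
| A] Data collection methods, pain | not limited (trial) | not limited |

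The questionnaire sentence also conflicts with itself. It speaks of the retraction period, then starts that period at extraction: "during the whole retraction period from day of extraction till the end of retraction". No place in the protocol restricts the final report to the time after T0.

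**2. What lies between the two opening dates**

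From the clinical procedure: extraction, securing of anchorage, and the full levelling and alignment sequence, the same for both groups. Patients are allocated before levelling (II, C] Implementation), but the allocated mechanics begin only after T0.

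**3. Whether the T0 pain form repairs this**

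The T0 records list a pain questionnaire, but the text says only that it is handed out and explained. Completion at T0 is not stated. Even a completed T0 score would not take extraction and levelling pain out of a final report that still begins at extraction.

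**4. Direction**

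Suppose a share w of the reported score comes from the common phase and 1 − w from retraction. The common phase has expected difference zero between randomised arms, so

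expected observed difference = (1 − w) × true retraction-phase difference.

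The difference shrinks for any w above zero. No phase length is needed for the direction.

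**5. Size: illustration only**

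The protocol gives no pain SD, pain effect or phase lengths. F] Sample size calculation (difference 1.0, SD 0.76, 10 per group before drop-out) is not about pain and does not enter here.

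*Power.* Assume a two-sided t-test at 0.05, 15 per group, an SD not changed by the mixing, and a retraction-phase effect of 1.0 or 0.8 SD:

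| w | power, 1.0 SD | power, 0.8 SD |
|---|---|---|
| 0 | 0.75 | 0.56 |
| 0.10 | 0.66 | 0.48 |
| 0.25 | 0.51 | 0.36 |
| 0.50 | 0.26 | 0.19 |

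*Sample-size factor.* Assume instead that the score averages over time, with 4–8 months of levelling and 6–9 months of retraction. The retraction share f runs from 6/(8 + 6) = 0.43 to 9/(4 + 9) = 0.69. With equal variance in the two phases and within-patient correlation ρ between them, the factor by which the sample size would have to grow is

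[f² + (1 − f)² + 2ρf(1 − f)] / f².

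- ρ = 1 (SD unchanged): 1/f² = 2.1 at f = 0.69 and 5.4 at f = 0.43.
- ρ = 0: 1.2 at f = 0.69 and 2.8 at f = 0.43.

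The range 1.2 to 5.4 comes entirely from the assumptions. It shows that the size is unknown, not what it is.

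**The case against.** The strongest reply is that this is a slip of wording. The sentence limits itself to the allocated technique and to the retraction period, levelling is not part of the allocated technique, and the questionnaire items are not in the protocol (the appendix shows only the VAS heading). The form actually used may therefore ask about retraction alone. That is possible, but the protocol does not say so. The sentence names extraction as the start, and the two other descriptions are wider still.

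Several stronger readings are tempting, and the objection to each stands:

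- A reader might infer that pain from miniscrew placement enters the score. Placement precedes extraction, so unless both fall on the same day only lingering soreness could be included.
- A reader might infer that pain before T0 is identical in the two arms. The treatment is identical; the pain is equal only in expectation. Patients are allocated before levelling and only assessors are blinded, so chance and individual differences remain.
- A reader might infer that pain is recalled once, at the end. The timeline and the harms paragraph point to a final questionnaire, and the list of tasks at the 4-weekly visits has no pain score. But a pain form is handed out at T0, and the outcome table speaks of scoring sheets in the plural. The protocol does not settle how often pain is scored.
- A reader might quote a two- to five-fold loss in sample size. That rests on assumed phase lengths, a time-averaged score and an unchanged SD. With uncorrelated phases the same lengths give 1.2 to 2.8.

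It is also fair that pain is one of several secondary outcomes and does not drive the sample size.

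**Conclusion.** The contradiction stands on the text alone. The questionnaire window opens at extraction; the objective and the common outcome window open at the start of retraction; a full phase with the same treatment in both arms lies between. Followed as written, the questionnaire adds noise and is expected to pull the between-arm pain difference toward zero. This rests on one assumption: that patients answer about the window that the protocol describes.

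The size cannot be derived from the protocol, and the illustrative figures should not be quoted as estimates. Nor do the documents support a claim of bias in favour of one technique, since randomisation makes the shared phase equal in expectation. Only the pain outcome is affected. Anchorage loss by CBCT between T0 and T1 is untouched. The point is worth correcting before patients complete the form, but it does not threaten the trial's main conclusion.

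**What to change.** 1. In C] Interventions, post-retraction questionnaire, replace the day of extraction with the start of retraction (T0) as the opening of the reporting window.
2. Bring E] Participant timeline, item 12, and the pain item under A] Data collection methods to the same T0–T1 window, and check that the printed questionnaire matches.
3. State that the pain form handed out with the T0 records is also completed at T0, so that the T0–T1 difference set in D] Outcomes can be formed for pain.

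Optionally, have patients mark the same 10-cm line at the existing 4-weekly visits, which would lessen the reliance on recall.

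The cost is three short wording edits and one form completed at a visit that already takes place, with no extra visits or patients. The optional marks would take about a minute each at scheduled visits.

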### **Outcome measure:**

	Outcome Name	Measuring Tool	Measuring Unit
Primary Outcome	Anchorage loss	CBCT	

- Linear measurement in mm

Angular measurement in degrees

Secondary Outcome	Rate of space closure	Digital scanned Dental Model	

- Scanned digital models in (mm)

○ Models taken every month

○ Analysed using 3 Shape Software

	Pain	Pain scoring sheets given to patients	VAS scoring from 1-10 (Fig 1)

	Root resorption	CBCT	Scoring system of Levander and Malmgren[39] (5 grades classification)
	Torque of anterior teeth	CBCT	Degrees
	Tip of anterior teeth	CBCT	Degrees
	Vertical position	Digital scanned Dental Model	Mm
	1 st Permanent Molar rotation	Digital scanned Dental Model	Degrees

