### **III) Data collection, management and analysis:**

#### **A] Data collection methods:**

##### ***Primary outcomes:***

**1. Anchorage loss:** will be accessed by the principal investigator via CBCT taken before and after the completion of retraction by identifying the landmarks, reference lines and planes, then will interpret the measurements in degrees and millimeters.

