##### ***Secondary outcomes:***

**1. Retraction rate:** to assess the antero-posterior movement of anterior teeth and first molars, the principle investigator will take study models for every participant monthly during the follow up visits. Then will digitize the models and identify the landmarks, reference lines and planes on the pre, interim and post-retraction digital dental models for measurements reading. Also, by identifying the landmarks, reference lines and planes using CBCT taken before and after the completion of retraction.

**2. Pain:** each patient will fill a questionnaire regarding his treatment experience in a Visual Analog Scale (VAS) scoring from 1-10 by making a handwritten mark on a 10-cm line that represents a continuum between “no pain” on the left end (0 cm) of the scale and the “worst pain” on the right end of the scale (10 cm). The questionnaire will include several questions related to oral hygiene, pain and discomfort experienced throughout the trial.

**3. Root resorption:** will be accessed by the principle investigator via CBCT taken before and after the completion of retraction. The resorption will be identified using

scoring system of Levander and Malmgren that classifies it into 5 grades: 0, no root resorption; 1, mild resorption, with the root of normal length and only an irregular contour; 2, moderate resorption, with small areas of root loss and the apex having an almost straight contour; 3, severe resorption, with loss of almost one third of root length; and 4, extreme resorption, with loss of more than one third of the root length.

**4. *Anterior teeth torque:*** will be accessed by the principle investigator via CBCT taken before and after the completion of retraction. The principal investigator will identify the landmarks, reference lines and planes, then will interpret the measurements in degrees.

**5. *Anterior teeth extrusion/intrusion:*** will be accessed by the principle investigator via CBCT taken before and after the completion of retraction. The principal investigator will identify the landmarks, reference lines and planes, then will interpret the measurements in millimeters.

**6. *Anterior teeth tip:*** will be accessed by the principle investigator via scanned digital models taken before and after the completion of retraction.

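### The primary outcome, anchorage loss, is not fixed as one variable: two unranked units, two instruments, and a sample size tied to neither

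*Protocol*

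**What the plan says.** **Outcome measure table.** The single primary outcome is anchorage loss, with CBCT as the tool. Two units are listed together: "Linear measurement in mm" and "Angular measurement in degrees".

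**III) A] Data collection methods, Primary outcomes.** Anchorage loss is again read from CBCT before and after retraction. The investigator identifies landmarks and planes, "then will interpret the measurements in degrees and millimeters". Neither unit leads.

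**C] Interventions, Follow up visits and Retraction records.** The four-weekly impressions are given the purpose of determining anchorage loss. At the end of retraction, "The final dental model will be used to assess the rate of retraction and molar anchorage loss achieved throughout the study". The final CBCT is taken to "acquire the final cone-beam CT to assess the movement and inclination of anterior teeth"; molars are not mentioned.

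**III) A], Secondary outcomes, item 1 (Retraction rate).** The item begins "to assess the antero-posterior movement of anterior teeth and first molars, the principle investigator will take study models for every participant monthly" and ends "Also, by identifying the landmarks, reference lines and planes using CBCT taken before and after the completion of retraction".

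**D] Outcomes.** "All outcomes will be assessed as the difference between T0 at the start of retraction and T1 after complete space closure".

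**F] Sample size calculation.** The trial is sized for one continuous response with SD 0.76 and a difference of 1.0, at 0.05 and power 0.8. This gives 10 per group, raised to 15 for drop-out. The response has no name, unit or instrument.

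**The concern.** A primary outcome has to be one variable, so that one comparison at 0.05 answers the research question. Here at least three readings could claim the name: the CBCT linear change, the CBCT angular change, and the linear change on dental models. The CBCT molar reading in millimetres also falls under a secondary outcome. Nothing in the text says which reading decides the trial, so that choice could be made once the results are known.

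The sample size section does not settle it. The null hypothesis concerns anchorage loss, so a reader can infer that this is the response meant, but not whether 1.0 is in millimetres or degrees, or whether it is read on CBCT or models. The stated error rate and power are then not attached to a defined variable.

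A lesser inconsistency has the same form. Tip of anterior teeth is CBCT in the outcome table but digital models in data collection, and vertical position is the reverse. This leaves two secondary outcomes unclear but does not affect the primary error rate or power.

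**Working it through.** **1. The sections side by side**

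| Section | Reading | Instrument | Unit |
|---|---|---|---|
| Outcome measure table, primary | Anchorage loss | CBCT | mm and degrees |
| Data collection, primary | Anchorage loss | CBCT | degrees and mm |
| Follow up visits | Anchorage loss | Impressions every 4 weeks | not stated |
| Retraction records | Molar anchorage loss | Final dental model | not stated |
| Data collection, secondary item 1 | First-molar antero-posterior movement | Monthly models, also CBCT | not stated |
| D] Outcomes | Anchorage loss, T0 to T1 | not stated | not stated |
| F] Sample size calculation | Unnamed continuous response | not stated | not stated |

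Timing is settled by D] Outcomes. Instrument and unit are not.

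**2. The Protocol's own sample size**

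Inputs from F] Sample size calculation: difference 1.0, SD 0.76, type I error 0.05, power 0.8. A two-sided test is assumed, because sidedness is not stated.

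- Standardised difference: d = 1.0/0.76 = 1.316.
- Normal approximation: n = 2(1.960 + 0.842)² × 0.76²/1.0² = 2 × 7.85 × 0.5776 = 9.07, rounded up to 10 per group.
- Exact two-sample t-test (noncentral t): n = 10.12. Power is 0.795 at 10 per group and 0.935 at 15 per group.

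The stated 10 per group reproduces, so the arithmetic is not at fault.

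**3. What the calculation guarantees without a named variable**

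Solving the same t-test for the difference that gives 80% power:

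- 10 per group: 1.325 SD.
- 15 per group, no drop-out: 1.060 SD.

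This is all the document supports: 80% power at these multiples of the SD of whichever variable is meant.

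**4. If 0.76 is not the SD of the variable finally used**

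The difference is held at 1.0 and the SDs are assumed, to show the range:

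| Assumed SD | n per group for 80% power | Power at 15 per group |
|---|---|---|
| 0.76 (Protocol) | 10 (exact 10.12) | 0.94 |
| 1.0 | 17 | 0.75 |
| 1.5 | 37 | 0.42 |
| 2.0 | 64 | 0.26 |

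**5. The unranked units**

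Suppose success in either CBCT unit counted, each tested at 0.05. With no true difference and jointly normal statistics, the chance of at least one false positive is greatest at zero correlation:

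1 − 0.95² = 0.0975, or 9.8%.

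Simulated t-tests with 10 per group (200,000 trials) gave 0.097. Readings from the same scans are probably correlated, which lowers the figure towards 5%.

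**6. Models instead of CBCT**

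The document gives no error variance or agreement between the two instruments, so this effect cannot be calculated.

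**The case against.** - **The two defining sections agree.** The outcome table and the primary data collection paragraph both name CBCT, and C] Statistical Analysis has data extracted from CBCT before and after retraction. The model sentence could describe an extra serial reading. This narrows the instrument conflict and shows which way to resolve it. It does not remove the conflict, because the procedural section assigns anchorage loss to impressions or models twice.
- **The stated purpose of the final CBCT is not a full list.** It also omits root resorption, which the Protocol assigns to CBCT elsewhere. That is fair: the omission of molars is weak evidence alone and only supports the explicit model sentence.
- **Molar movement under retraction rate may only be an input to space closure.** This is possible, since the CBCT sentence names no tooth. But it continues an item about anterior teeth and first molars, so the natural reading is that it covers both.
- **Millimetres are the likelier unit for 1.0.** The literature review quotes an anchorage difference in millimetres, and the assessor disagreement limit is one millimetre. This is plausible but remains an inference. The Protocol's summary of the study cited for the sample size concerns upper-incisor retraction and gives no anchorage-loss figure.
- **An analysis plan, or the figure not shown under D] Outcomes, may hold more detail.** Landmarks, and possibly a ranking of units, could be there. Neither would reconcile the Protocol's conflicting statements.
- **The 9.8% is only a ceiling under a rule the Protocol does not state.** Agreed; it is an illustration only.

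**Conclusion.** The concern holds. The Protocol fixes when anchorage loss is compared, but not one unit, and it contradicts itself on the instrument. Its sample size is correct arithmetic for an unnamed response: 79.5% power at 10 per group for 1.32 SD, two-sided test assumed.

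The demonstrable consequence is that the 5% error and 80% power are not attached to a defined primary variable, and that the deciding reading could be chosen late. The 9.8% bounds the effect of the unranked units only, under an either-unit rule. The loss of power if 0.76 is the wrong SD depends on assumed values. The swapped instruments for tip and vertical position are real but secondary.

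Confidence is high on the unranked units, the model-versus-CBCT conflict and the unnamed sample size variable. It is somewhat lower on the double listing of molar movement, which rests on the natural reading of one item.

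**What to change.** 1. Name one primary variable with tooth, direction, unit and instrument. One example is mesial displacement of the first molar in mm on CBCT from T0 to T1, compared between groups once at 0.05.
2. Make the angular and the model-based molar readings secondary.
3. Align Follow up visits and Retraction records with the outcome table and the primary data collection paragraph, including the stated purpose of the final CBCT.
4. In the retraction-rate item, remove CBCT first-molar movement or cross-refer it to the primary outcome.
5. In F] Sample size calculation, state the variable, unit and instrument behind 1.0 and 0.76. If they do not describe the named primary variable, restate the power for it.
6. Give one instrument each for tip and vertical position in the table and in data collection.

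The cost is wording in these sections and one check of the source of 1.0 and 0.76. CBCT and models are already taken at T0 and T1, so no new records are needed. The angular and model readings lose any claim to primary status. The one possible larger cost is that, if the two figures prove not to fit the chosen variable, the planned number of patients may need to be reconsidered.
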